5.7.4. Physical Examination and Neurological Examination

Clinically significant abnormalities found at a physical examination or neurological examination will be reported as AEs and will be included in the analyses of AEs.

5.7.5. Electrocardiograms

The 12-lead electrocardiograms (ECG) data will be summarized using shift table based on subjects with at least one post-baseline ECG assessment and whose baseline ECG assessment was not abnormal. This includes shift from normal or unknown at baseline to abnormal post-baseline, shift from normal or unknown at baseline to not adverse event or abnormal post-baseline, and shift from normal or unknown at baseline to adverse event post-baseline.

The number and percentage of subjects with shifts to abnormal ECG, not adverse events, and subjects with shift to abnormal ECG, adverse events at any time during post-baseline will be summarized. The ECG outlier in the uncorrected QT and Fridericia's corrected QTc intervals are the values exceeding a threshold of particular concern in clinical trials and are defined using criteria listed in FDA guidance - E14 Clinical Evaluation of QT/QTc Interval Prolongation and Proarrhythmic Potential for Non-Antiarrhythmic Drugs. The number and percentage of subjects

with ECG outlier in the uncorrected QT and Fridericia's corrected QTc interval will be summarized by treatment group.

- Absolute QTc interval prolongation:
 - \circ OTc interval > 450
 - o QTc interval > 480
 - o QTc interval > 500
- Change from baseline in QTc interval:
 - O QTc interval increases from baseline > 30
 - O QTc interval increases from baseline > 60

Baseline is defined in a similar way as with clinical laboratory data. The worst post-baseline value of each subject will be used.

5.7.6. Immunogenicity

5.7.6.1. Background

Definition of baseline value

Baseline value is defined as the latest immunogenicity data collected prior to the first dose. If no immunogenicity data are collected prior to the first dose, baseline value will be treated as antidrug antibody (ADA) negative for immunogenicity analyses.

A summary of treatment-emergent anti-aducanumab positive responses will also be presented using the following definitions:

Post-baseline positive anti-aducanumab antibody responses are defined as treatment-emergent if a subject is either (1) antibody negative at baseline; or (2) antibody positive at baseline but the post-baseline antibody response is more than 2-fold increase in titer compared to the baseline response.

Persistent and transient positive responses for the placebo-controlled period:

Subjects with treatment-emergent positive anti-aducanumab antibody responses in the placebocontrolled period will be further classified as transient positive under the following conditions:

- if only a single positive evaluation occurs which is not at the last available time point
- or if more than 1 positive evaluation occurs < 112 days (16 weeks) apart and there is at least 1 evaluation occurs thereafter;

Subjects with treatment-emergent positive anti-aducanumab antibody responses in the placebocontrolled period will be further classified as persistent positive under the following conditions:

- if more than one consecutive positive evaluation occurs ≥ 112 days (16 weeks) apart
- or if a single positive evaluation occurs at the last available time point with no further negative results available

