5.1. General Principles

5.1.1. High Level Description of Analyses

This SAP defines the analysis scope for FA. This SAP document supersedes the statistical section in the protocol and provides details for those analyses pre-specified before any planned study unblinding of the Biogen/IQVIA blinded team and before the final database lock. Additional ad hoc analyses may be conducted if needed after data unblinding at the final database lock. If there are any significant modifications in the SAP after data unblinding at the final database lock, those must be documented in the clinical study report accordingly.

Summary tables will be presented using descriptive summary statistics. For continuous endpoints, summary statistics will generally include number of participants with data, mean, standard deviation, median, 25% percentile, 75% percentile, minimum and maximum. For categorical endpoints, this will generally include number of participants randomized or dosed, number with data, and the percent of those with data in each category.

As mentioned in Section 1., due to the early termination of the study, an abbreviated CSR is planned. Accordingly, many endpoints will not be summarized. The data that will be summarized are full safety data, and data on disposition, baseline, demographics, exposure, protocol deviations and CDR-SB. Also, any listings that are routinely produced for Biogen clinical studies will not necessarily be mentioned in this SAP.

There will be no statistical testing for any endpoints.

The statistical software, SAS® version 9.4 or above will be used for all summaries and analyses.

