5.7.6.2. Immunogenicity analysis

Immunogenicity analysis set will be used for immunogenicity analysis. Tables will be presented by treatment group. Listings will be presented by treatment group stratified by ApoE status.

A summary table will be presented showing the number of subjects with treatment-emergent anti-aducanumab antibody positive response at any time post-baseline, the number of subjects with treatment-emergent anti-aducanumab antibody positive response at each visit, the number of subjects with persistent and transient response, the number of subjects positive at baseline with a treatment-emergent response and without a treatment-emergent response, and the number of subjects positive post-baseline or at baseline (with or without a treatment-emergent response). A listing of immunogenicity assessments as well as a listing of adverse events for subjects with any anti-aducanumab antibody positive results will also be provided.

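### Read literally, the SAP's persistent/transient antibody rule leaves some treatment-emergent positives in neither class (minor, wording only)

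*SAP*

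**What the plan says.** SAP 5.7.6.1, under "Persistent and transient positive responses for the placebo-controlled period", divides participants with a treatment-emergent positive response into two classes.

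Transient:
- T1: "if only a single positive evaluation occurs which is not at the last available time point"
- T2: "or if more than 1 positive evaluation occurs < 112 days (16 weeks) apart and there is at least 1 evaluation occurs thereafter"

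Persistent:
- P1: "if more than one consecutive positive evaluation occurs ≥ 112 days (16 weeks) apart"
- P2: "or if a single positive evaluation occurs at the last available time point with no further negative results available"

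There is no residual class, here or elsewhere. Protocol 12.6.2 says only that treatment-emergent antibodies will be summarized. The summary table in SAP 5.7.6.2 gives "the number of subjects with persistent and transient response", alongside any-time and by-visit counts of treatment-emergent positives. The same section plans "A listing of immunogenicity assessments". SAP 5.1.1 adds: "There will be no statistical testing for any endpoints".

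**The concern.** A two-class rule should give each treatment-emergent positive exactly one class. This one does not, and it produces an odd ordering: one positive at the last sample makes a participant persistent, but adding an earlier positive less than 112 days before it removes the participant from both classes. More evidence of a sustained response should not do that.

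If the rule is programmed as written, persistent plus transient can fall short of the treatment-emergent total. If it is programmed by interpretation, two programmers can reasonably produce different tables. Immunogenicity is one of the few objectives that the SAP keeps after termination (SAP 2.1), so the table will be reported.

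**Working it through.** There is no planned figure to reproduce. The check applies the four conditions to concrete sample histories.

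**Inputs**
- Threshold: 16 weeks × 7 = 112 days (SAP 5.7.6.1).
- Antibody target days: Week 12 = 85, Week 24 = 169, Week 52 = 365, Week 78 = 547 (SAP 9.1.4).
- Visit tolerance: ±3 days (Protocol 1.3, Table 1).
- Revised ET visit: 0 to 30 days after last dose. Revised follow-up: 84 ± 3 days after last dose. Both take an antibody sample (SAP 2.2.5 and its Table 1).
- Assumption: 'apart' means days from first to last positive. Each history below that meets no condition has exactly two positives, so a pair-by-pair reading gives the same result.

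**Spacings**
- Week 12 to Week 24: 169 − 85 = 84 days. With ±3 days at each visit, 84 ± 6 = 78 to 90. Always under 112.
- ET to follow-up: shortest (84 − 3) − 30 = 51; longest (84 + 3) − 0 = 87. Always under 112.
- Week 12 to Week 52: 365 − 85 = 280. Over 112.

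**Histories against the four conditions**

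| History | T1 | T2 | P1 | P2 | Class |
|---|---|---|---|---|---|
| R: Week 12 negative, Week 24 positive and last | no, at last sample | no, one positive | no, one positive | yes | persistent |
| A: Weeks 12 and 24 positive, Week 24 last | no, two positives | no, nothing later | no, 84 < 112 | no, two positives | none |
| B: only ET and follow-up positive, follow-up last | no, two positives | no, nothing later | no, 51–87 < 112 | no, two positives | none |
| C: Week 12 positive, Week 24 negative, Week 52 positive, Week 78 negative | no, two positives | no, 280 ≥ 112 | no, if 'consecutive' excludes the negative | no | none |

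History A can occur. A participant who withdraws consent has no ET visit (Protocol 8.3), and one who starts an outside disease-modifying treatment has no further visits (SAP 2.2.5, Table 1 footnote). Windowing does not change A, because Days 85 and 169 fall in different windows.

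History B depends on two things that the SAP leaves open.
- *Period.* SAP 1 and 3.1 use 'placebo-controlled' for the treatment period, with follow-up after it, so follow-up may not count.
- *Windowing.* Take last dose at Week 28 (Day 197), ET at 197 + 30 = Day 227 and follow-up at 197 + 84 = Day 281. In SAP 9.1.4, Day 227 shares the Week 24 window (127 to 266) with Day 169. SAP 9.1 keeps the sample closest to target, so Day 169 stays and Day 227 drops out. Follow-up is then the only positive and is last, which is persistent. With actual samples the same participant has no class.

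History C depends on 'consecutive'. Even on the strict reading, an intermittent responder is persistent if one unbroken run of positives spans 112 days or more.

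**Which readings close the gaps**
- Any positive at the last sample is persistent: A and B close; C stays open.
- 'Consecutive' allows a negative between: C closes; A and B stay open.
- Both together: complete. A positive last sample is persistent. With a negative last sample, one positive is transient by T1, several spanning under 112 days are transient by T2, and several spanning 112 days or more are persistent.

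**The case against.** The best defence is that a sensible programmer would fill the gaps. If one positive at the last sample is persistent, surely two are; and 'consecutive' may be meant loosely. That reading is possible and makes the rule complete. But it relaxes two separate words, and the SAP states neither relaxation. SAP 5.1.1 presents the document as the place where details are fixed before unblinding and lock, so the choice belongs there.

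A second defence is that the period is the treatment period, so the ET/follow-up case does not arise. This removes history B but not the defect. For a last dose at Week 28, counting only samples up to that dose leaves Weeks 12 and 24, which is the setting of history A.

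A third is that little depends on it. This stands. The split is descriptive and belongs to a tertiary endpoint in an abbreviated report. Nothing is tested, the any-time and by-visit counts do not use it, and the planned listing would let a reader reclassify individuals. The objection settles the severity, but it does not make the table add up.

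A reader might also infer that the termination created the gap, because the revised ET and follow-up samples can never be 112 days apart. The documents do not support that. The Week 12 and Week 24 samples, 84 days apart, are part of the protocol's own schedule, so the gap is in the wording.

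**Conclusion.** The point holds as a minor wording defect. Read literally, SAP 5.7.6.1 does not classify every treatment-emergent positive, and the two counts in SAP 5.7.6.2 need not add to the total.

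The Week 12/Week 24 case is the firmest. It needs only that Week 24 is the last available sample, and it does not depend on follow-up, windowing or the meaning of 'consecutive'. The ET/follow-up case assumes that follow-up is in the period and that actual samples are used. The intermittent case assumes the strict sense of 'consecutive'.

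Two stronger conclusions are tempting and unsupported. One is that a sizeable share of antibody-positive participants would be lost from the table: the documents give no antibody incidence, and listing possible sample patterns says nothing about how often each occurs. The other is that persistence would be understated: which of the two counts falls short depends on the class that the sponsor intended, and the SAP does not say.

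**What to change.** Before database lock, amend SAP 5.7.6.1 so that each treatment-emergent positive has exactly one class. One wording that works:
- Persistent: positive at the last available sample, whatever came before; or first and last treatment-emergent positives at least 112 days apart, whether or not a negative falls between.
- Transient: every other treatment-emergent positive.

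Because transient is the remainder, this rule is exhaustive and exclusive by construction. Any equivalent wording would do, including a separate class for intermittent positives. Also state that 'apart' runs from first to last positive, whether the follow-up sample counts, and whether actual or windowed samples are used.

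The cost is two or three sentences and no new data. The downside is small: late-onset and intermittent positives count as persistent, which a table footnote can flag. If the change comes after lock and unblinding, it should be documented in the clinical study report, as SAP 5.1.1 requires for significant modifications.

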5.7.6.2. Immunogenicity analysis

Immunogenicity analysis set will be used for immunogenicity analysis. Tables will be presented by treatment group. Listings will be presented by treatment group stratified by ApoE status.

A summary table will be presented showing the number of subjects with treatment-emergent anti-aducanumab antibody positive response at any time post-baseline, the number of subjects with treatment-emergent anti-aducanumab antibody positive response at each visit, the number of subjects with persistent and transient response, the number of subjects positive at baseline with a treatment-emergent response and without a treatment-emergent response, and the number of subjects positive post-baseline or at baseline (with or without a treatment-emergent response). A listing of immunogenicity assessments as well as a listing of adverse events for subjects with any anti-aducanumab antibody positive results will also be provided.

5.7.7. C-SSRS

The Columbia Suicide Severity Rating Scale (C-SSRS) is an assessment that evaluates suicidal ideation and behavior.

A summary of post-baseline C-SSRS results will be presented showing:

- The number of subjects with at least one post-baseline C-SSRS assessment
- The number of subjects with suicidal ideation
- Number of subjects with suicidal behavior
- Number of subjects with suicidal ideation or behavior
- Non-suicidal self-injurious behavior

The listing of subjects with post-baseline suicidal ideation, suicidal behavior, or non-suicidal self-injurious behavior, the listing of subjects with post-baseline suicidal ideation, and the listing of subjects with post-baseline suicidal behavior will also be presented.

6. Changes from Protocol-Specified Analyses

On 31 January 2024, the early termination of Study 221AD305 was announced. Consequently, protocol-specified final analysis that was designed to verify the clinical benefit of aducanumab will not be performed; only the analyses described in Section 5 will be performed. All protocol pre-specified analysis that were designed to assess the safety of monthly doses of aducanumab will be performed. Specifically, the changes in the planned analysis are as follows:

6.1. Primary Endpoint, Key Secondary Endpoints and Secondary Endpoints

Primary endpoint CDR-SB will be summarized. There will be no statistical testing.

The protocol-specified key secondary endpoints and secondary endpoints will not be analyzed.

6.2. Tertiary Endpoints

Protocol specified tertiary endpoints individual items of the RUD-Lite and QoL-AD scores will not be analyzed.

Protocol specified tertiary endpoints serum concentrations and PK parameters of aducanumab over time will not be analyzed.

7. Summary of Changes from the Previous Version of the SAP

This section is not applicable as there is no previous version of the SAP.

8. References

221AD305 ENVISION Clarification Letter 16FEB2024 Final Signed

221AD305 Unblinding Plan v3.4 29APR2024

Morris JC. The Clinical Dementia Rating (CDR): current version and scoring rules. Neurology. 1993;43(11):2412–2414.

van Ginkel JR, SijtsmaK, van der Ark LA, & Vermunt, JK. Incidence of missing item scores in personality measurement, and simple item-score imputation. Methodology: European Journal of Research Methods for the Behavioral and Social Sciences, 2010; 6(1), 17-30.

9. Appendix

9.1. Visit Window

For analyses summarized by visit, data collected during all scheduled and unscheduled visits will be mapped to an appropriate analysis visit using the windowing scheme shown below. If there are 2 or more assessments available in the same analysis window for a participant, the assessment that is closest to the target visit day will be used for analysis. If there are 2 or more assessments in the same analysis window with the same distance from the target visit day, the later assessment will be used.

As illustrated in Section 2.2.2., there are changes in the timing and the assessments to be collected for the safety follow-up visit following the study early termination. Because of these changes, the visit window mapping will vary depending on whether the corresponding assessment is collected at the follow-up visit and if the participant has achieved Week 122 as of January 31, 2024. Specifically:

- (1) If an assessment is not collected in the revised safety follow-up visit, the visit window mapping is not impacted and will be the same for all participants
- (2) If an assessment is collected in the revised safety follow-up visit
 - a. For those participants who have reached Week 122 as of January 31, 2024, the visit window mapping will use the windowing scheme that assumes safety follow-up visit is at Week 122 (18 weeks after Week 104)

 Because Study 221AD305's first participant was randomized and dosed on July 27, 2022, the expected Week 122 visit would have occurred in November 2024. Therefore, as of January 31, 2024, there should be no participants who had Week 122 visit.
 - b. For those participants who have not reached Week 122 as of January 31, 2024, the visit window mapping will use the windowing scheme that the safety follow-up visit is Week 116 (12 weeks after Week 104).

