Study 221AD305, also called the ENVISION study, was designed as a Phase 3b/4 randomized, double-blind, placebo-controlled, parallel-group study to verify the clinical benefit of aducanumab (BIIB037) in participants with Alzheimer's disease (AD). The primary study objective was to verify the clinical benefit of monthly doses of aducanumab on Clinical Dementia Rating Sum of Boxes (CDR-SB) relative to placebo at Week 78. The total duration of the study for each participant was planned to be approximately 130 weeks, including a series of screening visits within 8 weeks before administration of the first dose of study treatment, and a 104-week placebo-controlled treatment period followed by a safety follow-up (FU) visit 18 weeks after the final dose of study treatment.

Participants were scheduled to receive IV infusions of aducanumab or placebo approximately Q4W for 104 weeks. Participants were randomized to receive aducanumab: placebo in a 2:1 ratio. Aducanumab was initiated with a 6-dose titration period prior to reaching the target dose of 10 mg/kg.

Early termination of the study was announced on 31 January 2024. The decision was not related to any safety or efficacy concerns. Enrollment in 221AD305 was halted immediately upon the announcement. As a result, the planned primary analysis and optional interim analysis that were outlined in the 221AD305 protocol version 2.0, dated 15 April 2022, will not be conducted. Biogen offered the study participants the option to continue to receive treatment in a blinded fashion until 1 May 2024 to allow study participants and their health care providers sufficient time to plan future treatment decisions. Study participants were required to perform an early termination (ET) visit within 30 days of their last dose and a safety FU visit 12 weeks after their last dose. Due to the early termination of the study, an abbreviated clinical study report is planned.

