2.1.1. Tertiary Objectives and Endpoints Related to Safety and Immunogenicity

- · To assess the safety of monthly doses of aducanumab
 - Incidence of AEs and SAEs
 - o Incidence of ARIA-E and ARIA-H
 - Clinical laboratory shifts in reported values
- To assess the immunogenicity of aducanumab
 - o Incidence of anti-aducanumab antibodies (Abs) in serum over time

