2.2.3. Study Conduct Following Announcement of Study Termination

On 31 January 2024, Biogen announced the early termination of Study 221AD305. The decision was not related to any safety or efficacy concerns. Enrollment in 221AD305 was halted immediately upon the announcement. At that time, over 1000 participants had been enrolled in the study.

Following early termination of the study, Biogen offered the study participants the option to continue to receive treatment in a blinded fashion until 1 May 2024 to allow study participants and their health care providers sufficient time to plan future treatment decisions.

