2.2.5. Changes to Study Execution Following Announcement of Study Termination

1) On 31 January 2024, it was announced that as the study is early terminated, participants enrolled in the study may continue receiving treatment until 01 May 2024. Screening and enrollment would be closed for the study. The participant and care partner, as applicable, should return to the site for a safety follow-up visit 30 days after their last dose. On 16 February 2024, Biogen released a document 221AD305 ENVISION Clarification Letter_16FEB2024_Final Signed, which updated the changes to study execution: Early Termination Visit: assessments and timing (Protocol Section 1.3, Table 2)

Due to the early termination of the study, all participants will be asked to complete this early termination (ET) visit, which, to reduce participant burden, will be limited to assessments related

to participant safety. These assessments are reported in Table 1. Participants should complete this ET visit within 30 days of their last dose of study treatment.

2) Follow-up/End of Study (FU/EOS) Visit: assessments and timing (Protocol Section 1.3, Table 2)

Due to the early termination of the study, all participants are asked to complete their Follow-up/End of Study visit (also referred to as the safety follow-up visit) at 12 weeks (+/- 3 days) after the participant's last dose of study treatment. Participants who wish to withdraw and not receive additional dosing through 01 May 2024 are still encouraged to have a safety follow-up visit 12 weeks from their last dose of study treatment. In addition, similar to the ET visit, the number of assessments that need to be completed is now reduced to lessen participant burden. These assessments are reported below in Table 1. If a participant has had their last dose of study treatment and it has been more than 12 weeks since their last dose and the participant has not had their safety follow-up, then they should complete a safety follow-up visit within 30 days, as defined in Table 1.

3) Substudies (Protocol Section 5.1)

Due to the early termination of the study, all the longitudinal substudies are terminated and samples will no longer be collected for amyloid PET, tau PET, at Weeks 52, 78, and 104/ET.

4) Management of participants who had already discontinued treatment and who were following the visit schedule defined in Table 3 (Protocol Section 1.3, Table 3)

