Due to the early termination of the study, participants who discontinued treatment but agreed to remain in the study and follow the abbreviated visit schedule will be asked to complete their ET visit within 30 days and their FU/EOS visit (safety follow-up) visit 12 weeks after their last dose. If they have already had an ET visit following their last dose of treatment, then the ET visit does not need to be repeated. If it has been more than 12 weeks since their last dose and the participant has not had their safety follow-up, then they should complete a safety follow-up visit within 30 days, as defined in Table 1.

5) Visits at Week 26, Week 50, and unscheduled for Change in AD Meds (Protocol Section 1.3, Table 1 and Table 2)

Due to the discontinuation of the Aduhelm program and the early termination of the study, the visits at Week 26, Week 50, and unscheduled for change in AD medication will no longer need to be conducted as only clinical efficacy assessments are collected at these visits.

Table 1 Revised Schedule of Activities for Early Termination Visit and Followup/End of Study Visit for the Terminated ENVISION Study

Study Assessments ¹	Early Termination Visit (within 30 days of last dose)	Follow up/End of Study Visit ^{2,3} (12 weeks after last dose +/- 3 days)
Body Weight	X	X
Urine Pregnancy Test ⁴	X	X

Study Assessments ¹	Early Termination Visit (within 30 days of last dose)	Follow up/End of Study Visit ^{2,3} (12 weeks after last dose +/- 3 days)
Physical Exam	X	X
Neurological Exam	X	X
12-Lead ECG	X	X
Vital Signs ⁵	X	X
Hematology, Blood Chemistry, and Urinalysis	X	X
Anti-Aducanumab Ab	X	X
Coagulation Panel	X X	
Brain MRI ⁶	X X	
C-SSRS-SLV	X X	
Concomitant Therapy and Procedures	Monitor and record continuously throughout the study	
SAE Reporting	Monitor and record continuously throughout the study	
AE Reporting	Monitor and record continuously throughout the study	

¹Clinical efficacy assessments (MMSE, CDR, ADAS-Cog13, ADCS-ADL-MCI, NPI-10, RUD-Lite, QoL-AD) have been removed from the Early Termination Visit and safety follow-up visit to reduce participant burden.

³If it has been more than 12 weeks since the participant's last dose, participants who had discontinued treatment early but had agreed to remain in the study (following the Table 3 Schedule of Activities in the protocol) should complete this Follow-up visit within 30 days of the clarification letter.

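### The safety follow-up is windowed by study day to a Week 116 row that no on-schedule visit can reach, so off-drug lab and ADA values appear under planned weeks or drop out of the by-visit tables

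*SAP*

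**What the plan says.** SAP 2.2.5 sets the revised follow-up (FU/EOS) "at 12 weeks (+/- 3 days) after" the participant's last dose, with an early termination (ET) visit within 30 days of last dose. SAP 2.2.5 Table 1 collects labs and ADA at both. Participants already off treatment and following protocol Table 3 "will be asked to complete their ET visit within 30 days and their FU/EOS visit" on the same 12-week basis. The announcement of 31 January 2024, before the clarification letter of 16 February 2024, had said that participants "should return to the site for a safety follow-up visit 30 days after their last dose".

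SAP 9.1 maps scheduled and unscheduled data to analysis visits by study day. Where several values share a window, the one nearest the target day is used, or the later one if tied. For participants not at Week 122 by 31 January 2024 (by the SAP's own reasoning, everyone), "the visit window mapping will use the windowing scheme that the safety follow-up visit is Week 116 (12 weeks after Week 104". The windows in Tables 7 and 9 are then:

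- Labs: Week 52, Days 2-546; Week 104, Days 547-770; Week 116, Day 771 onward.
- ADA: Week 12, Days 2-126; Week 24, Days 127-266; Week 52, Days 267-455; Week 78, Days 456-637; Week 104, Days 638-770; Week 116, Day 771 onward.

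No table has a row for ET or for time since last dose. SAP 3.3 ends the on-treatment period 28 days after the last dose.

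**The concern.** Week 116 equals 12 weeks after the last dose only for someone dosed to Week 104, and the SAP's own dates rule that out for everyone. SAP 9.1 checks the dates for Week 122 and concludes that no one should have had that visit, but it does not repeat the check for the replacement row.

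The cause is study-day windowing with no follow-up visit tied to last dose. The empty row is the visible symptom. The outputs at stake are the lab summaries and mean figures by visit (SAP 5.7.2) and ADA positivity at each visit (SAP 5.7.6.2). SAP 2.1.1 retains "Incidence of anti-aducanumab antibodies (Abs) in serum over time" as one of the few endpoints still reported. A reader of those tables would see Week 104 results in a study where no one could be dosed to Week 104. The Week 52 lab row would mix on-treatment values with values taken about 12 weeks off drug, and the row meant for follow-up would be blank.

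**Working it through.** **Inputs.** SAP 9.1: the "first participant was randomized and dosed on July 27, 2022". SAP 1: participants had "the option to continue to receive treatment in a blinded fashion until 1 May 2024". Study day = date - Day 1 + 1 (SAP 3.1). Follow-up at last dose + 84 days, +/- 3. ET at last dose + 1 to 30 days. Windows as in SAP Tables 7 and 9.

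**The plan's own figure.** Week 122 is Day 855. 27 July 2022 + 854 days = 27 November 2024, which matches the SAP's November 2024. The Week 116 cut-off also reproduces as a midpoint of target days: (729 + 813)/2 = 771.

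**Reach of the Week 116 row.**

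- 1 May 2024 is Day 645 (Week 92) for the first participant, the latest possible last dose.
- Latest on-schedule follow-up: 645 + 87 = Day 732.
- Shortfall: 771 - 732 = 39 days. Reaching the row needs a visit at least 771 - 645 = 126 days after last dose.
- Catch-up visits within 30 days of the 16 February 2024 letter end by Day 600.

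**Where the follow-up lab goes.** This takes each of the 24 Q4W last doses from Day 1 to Week 92, with ET and follow-up both on schedule and no Table 3 visits. The planned lab is on Day 365.

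| Last dose | Follow-up, study days | Result for follow-up lab | Last doses |
|---|---|---|---|
| Day 1 to Week 40 | 82-368 | Shown as Week 52 | 11 |
| Week 44 | 390-396 | Depends on ET date | 1 |
| Weeks 48-64 | 418-536 | In no row (ET or planned lab is nearer Day 365) | 5 |
| Weeks 68-92 | 558-732 | Shown as Week 104 | 7 |

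**Where the follow-up ADA goes.** The conditions are the same, with planned samples on Days 85, 169, 365 and 547.

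- Shown under a planned week for 15: Week 12 (last dose Day 1), Week 24 (Weeks 8-12), Week 52 (Weeks 28-40), Week 78 (Weeks 56-68), Week 104 (Weeks 80-92).
- In no row for 5: Weeks 20, 24, 48, 52 and 76.
- Dependent on the ET date for 4: Weeks 4, 16, 44 and 72.

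**Late entrants.** First dose on or after 1 July 2023 gives a last dose L of at most Day 306, before any planned Week 52 lab. An on-schedule follow-up is hardest to select when ET is at L + 30 and follow-up at L + 87. The follow-up is then nearer Day 365 if the midpoint L + 58.5 is at most 365, that is L at most 306. At L = 306 the distances are 393 - 365 = 28 and 365 - 336 = 29, so the follow-up is used. With both visits on schedule (or no ET), the Week 52 lab for this group is therefore at least 81 days after last dose, unless an unscheduled lab is nearer.

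**Share of participants.** SAP 2.2.3 says only: "At that time, over 1000 participants had been enrolled in the study". Assume uniform entry over the 554 days from 27 July 2022 to 31 January 2024. The late-entrant group is then 215/554 = 38.8%. With linearly rising entry it is 1 - (339/554)^2 = 62.6%, and with linearly falling entry (215/554)^2 = 15.1%.

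**The case against.** Study-day windowing is ordinary practice, and the Week 116 label does not itself move values. The Week 52 lab window is the same in the scheme for participants who reached Week 122, so anyone stopping early would be mapped this way regardless. That stands, and it is why the cause lies in the missing follow-up visit. It does not rescue the row, which the SAP introduced because the follow-up timing had changed.

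Some mixing is also protocol design. Protocol Table 3 collects labs at Weeks 50/52 and 104 from participants already off treatment, and the SAP does not limit by-visit tables to the on-treatment period. There is no statistical testing, and an immunogenicity listing is provided. All of this stands and limits the consequence.

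Three stronger readings are tempting, and the documents do not support them.

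- A reader might infer that everyone first dosed on or after 1 July 2023 who attends follow-up has an off-drug Week 52 lab. Late visits break this. With last dose on Day 306, ET on Day 334 and follow-up on Day 397, the distances to Day 365 are 31 and 32. The ET lab, 28 days after last dose and on-treatment, is then used. An ET on Day 338 likewise beats a follow-up on Day 393 (27 against 28).
- A reader might take 39% as the share affected. It rests on an assumed entry pattern, and the enrolled total is not a count of participants with follow-up labs.
- A reader might count ET values as part of the problem. Those within 28 days of last dose are on-treatment under SAP 3.3.

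**Conclusion.** The concern holds in this form: the Week 116 row can receive no on-schedule follow-up. Off-drug lab and ADA values from on-schedule 12-week follow-ups are shown under planned weeks or dropped from the by-visit tables.

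The empty row follows from the SAP's dates alone. The last-dose groupings assume Q4W dosing, on-schedule 12-week follow-up, ET attended within 30 days and no Table 3 visits. Eighteen-week follow-ups before the letter and catch-up visits map differently. The number of participants affected is undetermined: the late-entrant group alone could be 15% to 63% of those enrolled under the entry patterns tried.

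The damage is confined to descriptive by-visit lab summaries and figures and to ADA positivity at each visit. Adverse events, ARIA, potentially clinically significant labs, the hepatotoxicity evaluation, any-time ADA and persistent or transient ADA do not use these windows. SAP Tables 8 and 10 (vital signs and MRI) carry the same unreachable row, but the SAP specifies no by-visit summary for either.

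**What to change.** In SAP 9.1 Tables 7 and 9, and in Tables 8 and 10 for consistency:

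- Replace the Week 116 row with a safety follow-up (FU/EOS) analysis visit assigned by eCRF visit label. Report days since last dose with it, because follow-ups may have been done at about 30 days, 12 weeks, 18 weeks or as catch-up visits.
- Exclude FU-labelled records from the planned-week windows. The exception is a follow-up combined with a protocol-scheduled visit (protocol Table 2, footnote 4), which also counts for that week.
- Leave ET values taken within 28 days of last dose, and protocol Table 3 visits, in the planned-week windows.
- Flag any planned-week value taken more than 28 days after last dose.

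The cost is appendix wording and a little derived-visit reprogramming before database lock. No new data are needed. The planned-week rows will hold fewer values.
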